#### **5.3.3. Activity/Exercise**

Subjects will abstain from strenuous exercise for 30 minutes before the start of BP measurement and for 24 hours before each blood collection for clinical laboratory tests. Subjects may participate in light recreational activities (eg, watching television, reading).

### **5.4. Screen Failures**

Screen failures are defined as study participants who consent to participate in the clinical study, but are not subsequently randomly assigned to treatment/entered in the study. A minimal set of screen failure information is required to ensure transparent reporting of screen failure participants to meet the Consolidated Standards of Reporting Trials publishing requirements and to respond to queries from regulatory authorities. Minimal information includes demography, screen failure details, eligibility criteria, and any serious adverse event (SAE). Individuals who do not meet the Screening criteria for participation in this study (screen failures) may be rescreened up to 3 times.

## 6. STUDY DRUG ADMINISTRATION AND MANAGEMENT

### 6.1. Study Drug Administration

#### 6.1.1. Description of Study Drug

The study drug product is an immediate release formulation containing standard excipients generally recognized as safe including bulking agent, disintegrant, glidant, and lubricant that are compressed into a tablet. The MLS-101 tablet contains 12.5 to 100 mg of MLS-101 drug substance (as a free-base form: [REDACTED]). The MLS-101 tablet and matching placebo tablet are round, white, film-coated tablets with no identifying mark. MLS-101 tablets of 12.5 mg, 25 mg, and 100 mg and placebo tablets are packaged in either 30 count 60 cc white round high density polyethylene bottles with a child-resistant cap or polyvinyl chloride/Aclar blisters with foil backing and 7 tablets per blister strip. Packaged tablets will be assigned a unique identifying number, used by the interactive web response system (IWRS) to identify the content but maintaining the blind of the subject and site. The test materials will be identified by the lot, batch numbers, retest date, and certificate of analysis.

#### 6.1.2. Dosing and Administration

*Placebo Run-In:* In Part 1, upon signing the Screening/main study ICF, subjects will begin a single-blind (subjects blinded to treatment allocation), up to 2-week run-in period of BID oral treatment with placebo, while continuing to remain on stable doses of their background antihypertensive medications. Subjects will orally administer placebo morning and evening, approximately 12 hours apart. On site visit days, subjects should be instructed to take their morning dose of study drug at the site. In Part 2, upon signing the Screening/main study ICF, subjects will begin a single-blind (subjects blinded to treatment allocation), up to 2-week run-in period of QD oral treatment with placebo, while continuing to remain on stable doses of their background antihypertensive medications.

*8-Week Treatment Period:* In Part 1, subjects will orally administer the assigned study drug (MLS-101 [25 mg BID, 50 mg QD, 100 mg QD] or placebo) according to the assigned dosing regimen for 8 weeks beginning on Study Day 1. To maintain the integrity of the blind, all subjects (regardless of dosing group) will orally administer study drug morning and evening, approximately 12 hours apart; active drug is administered as the morning dose for all QD dose groups. Subjects will be monitored by ABPM for 24 hours before the first morning dose on Study Day 1 and for 24 hours after the morning dose on Study Day  $49 \pm 2$  days (end of Week 7). On site visit days, subjects should be instructed to take their morning dose of study drug at the site. In Part 2, subjects will orally administer the assigned study drug (MLS-101 [100 mg QD] or placebo) according to the assigned dosing regimen for 8 weeks beginning on Study Day 1. Subjects will be monitored by ABPM for 24 hours before the first morning dose on Study Day 1, for 24 hours beginning on Study Day  $28 \pm 2$  days (Week 4), and for 24 hours after the morning dose on Study Day  $49 \pm 2$  days (end of Week 7).

### 6.2. Preparation, Handling, Storage, and Accountability

#### 6.2.1. Study Drug Preparation

Not applicable.

### **6.2.2. Study Drug Packaging and Labeling**

PCI Clinical Services will label, pack and release study drug in accordance with the Clinical Trials Directive 2001/20/EC and Good Manufacturing Practice Directive 2003/94/EC for Investigational Medicinal Products.

As this is a double-blind study, labeling of the tablet package will not show the treatment allocation. All other information required by regulation will appear on the label.

### **6.2.3. Study Drug Handling and Disposal**

All study drug supplies are to be used only for this clinical study and not for any other purpose. Authorized study personnel must maintain a full record of study drug disposition (ie, a log by date received, dispensation date and subject, date of return from the subject, and detailed study drug usage by each study subject).

After reconciliation, used study drug will be returned according to instructions provided by the sponsor. At study conclusion, all remaining used supplies will be similarly returned and disposed. Authorized study personnel will record any unaccounted supplies in the final accountability records.

### **6.2.4. Study Drug Storage**

The study drug should be stored at room temperature (59°F to 77°F [15°C to 25°C]) in an approved storage area with access limited to authorized study personnel.

### **6.2.5. Study Drug Accountability**

Study drug (including placebo) will be maintained under adequate security by appropriate site personnel (eg, pharmacist) and in accordance with applicable regulatory requirements. Study drug remaining at the end of the study will be returned to the sponsor or their representative, or destroyed on behalf of the sponsor.

The investigator or designee must maintain adequate records of receipt and distribution of all study drug, using appropriate accountability records.

## **6.3. Randomization and Blinding**

All subjects who qualify for Part 1 based on inclusion/exclusion criteria and complete up to a 2-week Placebo Run-in period and 24-hour ABPM procedure will be randomized into 4 equal treatment groups (1:1:1:1) to 25 mg BID, 50 mg QD, 100 mg QD, or placebo; each treatment group will consist of approximately 30 subjects stratified by BP (seated SBP  $\leq$  160 mmHg and seated SBP  $>$  160 mmHg). All subjects who qualify for Part 2 based on inclusion/exclusion criteria and complete up to a 2-week Placebo Run-in period and 24-hour ABPM procedure will be randomized (5:1) to either 100 mg QD MLS-101 or placebo such that the MLS-101 treatment group will consist of approximately 30 subjects and the placebo treatment group will consist of approximately 6 subjects.. The sponsor will arrange for Randomization of study subjects by study drug dosage group and treatment assignment. Randomization numbers and study drug supplies will be assigned using IWRS. Access to the Randomization codes will be controlled and documented.

The study will be conducted in a double-blind manner so that neither the center personnel nor the subject is aware of which treatment is administered. The identity of study drug assignments (MLS-101 or placebo) will be concealed from the investigator, the subject, research center staff, and all personnel involved in the conduct of the study, with the exception of the unblinded sponsor drug management staff who will oversee the study drug allocations and IWRS/dispensing compliance at the study centers.

Except when it is essential for the medical management of the subject, unblinding the treatment assignment will be considered a protocol deviation. Emergency treatment allocation information will be available by secured access to the IWRS system. If possible, the investigator should contact the sponsor before unblinding any subject's treatment assignment. In the event that this is not possible, the sponsor should be notified within 24 hours after the unblinding event. After unblinding, the subject will be discontinued from study drug treatment and will undergo Study Week 8 (end-of-treatment) assessments. Subjects will be asked to return for final follow-up approximately 4 weeks later (ie, Study Week 12/end-of-study visit). The reason for unblinding must be documented in the eCRF.

#### **6.4. Study Drug Compliance**

Compliance with study drug will be assessed at each visit. Compliance will be assessed by direct questioning and counting returned tablets during the site visits and documented in the source documents and relevant case report form. Deviation(s) from the prescribed dosage regimen should be recorded.

A record of the quantity of study drug dispensed to and administered by each subject must be maintained and reconciled with study intervention and compliance records. Study drug start and stop dates, including dates for study drug delays and/or dose reductions will also be recorded.

#### **6.5. Dose Modification**

In general, if, at any time during the study, a subject meets 1 or more of the laboratory exclusion criteria for the study (eg, seated SBP  $\geq$  175 mmHg or DBP  $\geq$  100 mmHg, serum potassium  $>$  5.2 mEq/L, serum cortisol  $<$  3 mcg/dL), laboratory test values will be confirmed using a local lab and BP measurements will be repeated at home. If laboratory exclusion criteria are met, the subject's dose of study drug may be temporarily withheld, adjusted, or stopped by the investigator in consultation with the medical monitor. The subject will receive appropriate antihypertensive treatment if clinically indicated, and will remain in the study for further safety monitoring. Guidelines for dose reduction/stopping in the management of hyperkalemia are included in [Section 6.5.1](#). All subjects will be given dietary counseling to avoid foods high in potassium during the study ([Appendix 12.6](#)). Guidelines for the management of hypotension are included in [Section 0](#). In addition, serum cortisol levels will be monitored throughout the study, and all subjects will be monitored for signs and symptoms of adrenal insufficiency (ie, nausea, vomiting, light-headedness, low BP, or electrolyte abnormalities) at every study visit. Based on changes in cortisol levels, an ACTH stimulation test ([Appendix 12.7](#)) may be performed and the subject's dose of study drug may be stopped. Guidelines for potential dose discontinuation in the management of adrenal insufficiency are included in [Section 6.5.3](#).

### 6.5.1. Hyperkalemia

If serum potassium level is elevated at the central laboratory measurement, the following actions are to be taken:

- Serum potassium > 5.2 and ≤ 5.5 mEq/L: Retest at local lab to confirm. If potassium remains elevated, reduce the MLS-101 dose according to [Table 3](#) (first dose-reduced level). Wait 2 to 7 days, then retest. If potassium remains elevated, reduce the MLS-101 dose again according to [Table 3](#) (second dose-reduced level).
- Serum potassium > 5.5 and ≤ 6 mEq/L: Retest at local lab to confirm. If potassium remains elevated, hold dose. Wait 2 to 7 days, then retest. If potassium ≤ 5.2 mEq/L, resume dosing. If potassium > 5.2 mEq/L, continue to hold dose. Wait 2 to 7 days, then retest. If potassium ≤ 5.2 mEq/L after second retest, restart at first dose-reduced level according to [Table 3](#). If potassium > 5.2 mEq/L after second retest discontinue study drug.
- Serum potassium > 6 mEq/L: Hold study drug dose and bring subject in for an unscheduled study visit for safety ECG and serum potassium retest at local lab; subject attends next regularly scheduled visit. If potassium from local lab retest ≤ 5.2 mEq/L, resume dosing. If potassium > 5.2 mEq/L, contact the sponsor's medical monitor for further guidance.

Note: If a retest of serum potassium level falls into a higher range than the original test, follow the instructions for the higher potassium range.

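### After the first action, Protocol Section 6.5.1 can give two different instructions for one potassium result, and it does not name the dose at which held dosing resumes

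*Protocol*

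**What the plan says.** Protocol Section 6.5.1 opens in directive terms: "If serum potassium level is elevated at the central laboratory measurement, the following actions are to be taken". It then defines three ranges (mEq/L) and adds a Note.

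- **Above 5.2, up to 5.5.** After local confirmation, the instruction begins "If potassium remains elevated, reduce the MLS-101 dose according to" and points to the first level of the dose schedule. If potassium is still elevated 2 to 7 days later, the second level applies. No return to the assigned dose is described.
- **Above 5.5, up to 6.** After local confirmation the dose is held. The rule for the first retest, 2 to 7 days later, is "If potassium ≤ 5.2 mEq/L, resume dosing. If potassium > 5.2 mEq/L, continue to hold dose". The second retest comes after another interval of the same length. A subject who has normalised by then falls under "If potassium ≤ 5.2 mEq/L after second retest, restart at first dose-reduced level according to", with the level taken from the dose schedule. A subject who has not falls under "If potassium > 5.2 mEq/L after second retest discontinue study drug".
- **Above 6.** The drug is held at once, with an unscheduled visit for an ECG and a local retest. Dosing resumes if that retest is 5.2 or lower. Otherwise the site is to seek advice from the medical monitor; discontinuation is not mentioned.
- **Note.** For results that move up a range, the rule is "If a retest of serum potassium level falls into a higher range than the original test, follow the instructions for the higher potassium range".

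Protocol Section 6.5 is looser. It lets the investigator withhold, adjust or stop the drug in consultation with the medical monitor, and it describes Section 6.5.1 as guidelines.

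**The concern.** A site should be able to take a sequence of potassium values and arrive at one instruction. After the first action, two places in Section 6.5.1 fail that test.

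First, the discontinuation sentence in the middle range has no upper bound and no exception, so it covers a second retest above 6. The Note covers the same result and sends it to the top range.

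Second, the resumption sentence in the middle range is silent on dose, although the clause for the second retest is explicit about it.

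Subject safety is the main stake, since two sites could act differently on identical results. The data are affected too. SAP Section 6.3.5 summarises dose modifications and withdrawals by visit, and SAP Section 6.7.1 tabulates adverse events leading to either. SAP Section 6.4.1.1 imputes the baseline SBP when treatment is withdrawn with the reason recorded as adverse event or physician decision. A hold or a dose reduction is not among the listed intercurrent events.

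**Working it through.** The plan gives no figure to reproduce. The check follows example sequences through the text.

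**Inputs.** The ranges and Note come from Protocol Section 6.5.1. Table 3 gives the dose steps: 25 mg BID to 12.5 mg BID to 0; 50 mg QD to 12.5 mg QD to 0; 100 mg QD to 50 mg QD to 25 mg QD.

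| Sequence (mEq/L) | Text of the range alone | With the Note |
|---|---|---|
| Confirmed 5.3, then 5.0 | First reduced level, no stated route back | Same |
| Confirmed 5.3, then 5.3 | Second reduced level | Same |
| Confirmed 5.8, then 5.0 | Hold, then resume; no level named | Same |
| Confirmed 5.8, 5.4, 5.0 | Hold, then first reduced level | Same |
| Confirmed 5.8, 5.4, 5.3 | Hold, then discontinue | Same |
| Confirmed 5.8, 5.4, 6.1 | Hold, then discontinue | Hold, ECG, local retest; resume if 5.2 or lower, otherwise contact the medical monitor |
| Confirmed 5.8, then 6.1 | Keep holding, retest in 2 to 7 days | Keep holding, unscheduled visit, ECG, local retest |

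The pattern is the same in all three active regimens of Table 3.

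**Second retest.** Rows five and six differ only in the last value. At 5.3 discontinuation is the sole instruction. At 6.1 there are two, and under the Note the higher value gets the less final one. The second retest falls 2 + 2 = 4 to 7 + 7 = 14 days after the hold begins. At the first retest (last row) both routes keep the hold; only timing and procedures differ.

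**Resumption dose.** Compare rows one and three, both normalised. If resumption means the assigned dose, the ratio of the middle-range dose to the lower-range dose is:

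- 100 mg QD: 100 / 50 = 2
- 25 mg BID: 25 / 12.5 = 2
- 50 mg QD: 50 / 12.5 = 4

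If resumption means the first reduced level, each ratio is 1. The text does not say which.

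**Effect on the primary analysis.** If the drug is discontinued for one of the two recorded reasons above, the Week 8 value becomes the baseline value, so that subject's change is 0. If the drug is held and later resumed, with no other intercurrent event, the observed value is used. For scale only, treat the arm mean as a simple average of 30 subjects (the planned number per arm). Replacing one subject's change d by 0 moves the mean by d / 30. The documents do not give d for such a subject; assuming 5 to 20 mmHg, the shift is 5 / 30 = 0.17 to 20 / 30 = 0.67 mmHg. The planned precision in the protocol synopsis is ±3.8 mmHg.

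**The case against.** The best defence is that the algorithm is graded and the Note already settles precedence. The first actions do rise with potassium: reduce after confirmation, hold after confirmation, hold at once with an ECG. At the disputed second retest the subject is off drug on either route, and the medical monitor can still stop treatment. A hold followed by rechallenge, set against a reduction without a hold, can also be a deliberate clinical choice.

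Most of this stands, and it limits the point. It does not remove it. The Note does not exempt the discontinuation sentence, and giving the Note precedence produces the reversal between 5.3 and 6.1. The looser wording of Section 6.5 does not settle the matter either, because Section 6.5.1 is written as required action.

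Several stronger readings are tempting but unsupported:

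- *The whole algorithm runs against severity.* It does not; only later steps are affected.
- *The protocol states that a resolved 5.8 returns to full dose.* It names no dose; that is inferred from the contrast with the next clause.
- *On 100 mg QD the gap is fourfold (100 against 25 mg).* That sets a resolved case against an unresolved one, since 25 mg is reached only if potassium stays elevated.
- *A confirmed value above 6 may simply resume.* Resumption there requires a local retest of 5.2 or lower, so the high value was not confirmed.
- *Hyperkalemia is named as the main dose-limiting risk.* Protocol Section 8.3.7 lists hyperkalemia with dose modification as one of three events of special interest, without ranking. A hold already meets that definition, so the count of such events does not turn on the disputed sentences.

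**Conclusion.** The point holds in this limited form. Section 6.5.1 gives two instructions for a second retest above 6 in a subject held for a confirmed value above 5.5 and up to 6. It also leaves the resumption dose after the first retest unstated. The first defect follows directly from the text. The second is certain as an omission; the twofold contrast on 100 mg QD depends on reading the resumption sentence as a return to the assigned dose.

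The documents give no frequency for either path, so the number of subjects affected is unknown and no distortion of the Week 8 result is shown. The effect on the primary analysis is a possible route for individual subjects, small per subject on the assumptions above. The reason to correct the text is that a directive safety rule should not permit two actions on one laboratory result.

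**What to change.** The sponsor should reconcile, within Protocol Section 6.5.1:

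1. the discontinuation sentence for the second retest with the Note and with the instructions for values above 6;
2. the resumption sentence after the first retest with the clause that names the first reduced level, and with the range above 5.2 up to 5.5, where no route back is stated.

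The aim is that each potassium result leads to one instruction. Which rule and which dose apply is for the sponsor to decide. The directive wording of Section 6.5.1 and the discretionary wording of Section 6.5 should be aligned at the same time.

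The cost is a short protocol clarification. No visits or samples are added.

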**Table 3: MLS-101 Dose Reduction Schedule**

Assigned Dose Level	First Dose-reduced Level	Second Dose-reduced Level
25 mg BID	12.5 mg BID	0
50 mg QD	12.5 mg QD	0
100 mg QD	50 mg QD	25 mg QD

BID = twice daily; QD = once daily

### 6.5.2. Hypotension

#### 6.5.2.1. Orthostatic Hypotension

Standardized assessment of standing BP will be performed at Screening/start of Placebo Run-in, Randomization, Study Week 1, and Study Week 8 as described in [Appendix 12.5](#). In addition, assessment of standing BP will be performed if a subject reports symptoms of hypotension (eg, light-headedness, dizziness, presyncope, or syncope) during the study, and the standing BP measurement will be assessed weekly for these subjects until symptoms resolve.

Orthostatic hypotension is defined as a decrease in SBP ≥ 20 mmHg or DBP ≥ 10 mmHg from sitting to standing position within 3 minutes of standing. If subjects experience orthostatic hypotension with symptoms (eg, light-headedness, dizziness, presyncope, or syncope) during the study, it will be medically managed by the investigator; adjustment to background therapy and/or dose reduction of study drug according to [Table 3](#) may be considered.

If subjects experience orthostatic hypotension during Screening/start of Placebo Run-in, measurement may be repeated during the Screening period to be eligible for study enrollment, and background therapy may be adjusted at the investigator's discretion.

### **6.5.2.2. Symptomatic Hypotension**

If subjects experience symptoms of hypotension (eg, light-headedness, dizziness, presyncope, or syncope) during the study, it will be medically managed by the investigator; adjustment to background therapy and/or dose reduction of study drug according to [Table 3](#) may be considered.

### **6.5.3. Adrenal Insufficiency**

Serum cortisol levels will be measured at Screening/start of Placebo Run-in, Randomization, Study Weeks 1, 2, 3, 4, 5, 6, 7, 8, and at the follow up visit (Study Week 12). Cortisol assessment should occur before 10 am on the morning of the study visit. In addition, subjects should be monitored for signs and symptoms of adrenal insufficiency (ie, nausea, vomiting, light-headedness, low BP, or electrolyte abnormalities) at every study visit. If adrenal insufficiency is suspected, glucocorticoid replacement therapy should be initiated until adrenal insufficiency can be ruled out.

Based on morning cortisol level at the central laboratory measurement, the following actions are to be taken:

- Serum cortisol  $\geq$  18 mcg/dL: No action required.
- Serum cortisol  $\geq$  3 and  $<$  18 mcg/dL: If there are no signs or symptoms of adrenal insufficiency (see above), then no action is required. If signs or symptoms of adrenal insufficiency are observed, then an ACTH stimulation test should be performed as described in [Appendix 12.7](#) to rule out adrenal insufficiency. If there is no evidence of adrenal insufficiency based on ACTH stimulation test results, then continue at current dose. If ACTH stimulation test is abnormal, then study drug should be discontinued. ACTH stimulation test may be waived with sponsor's approval.
- Serum cortisol  $<$  3 mcg/dL: If at any time during the study serum cortisol  $<$  3 mcg/dL, then measurement should be repeated. If confirmed, then an ACTH stimulation test should be performed as described in [Appendix 12.7](#) to rule out adrenal insufficiency. If there is no evidence of adrenal insufficiency based on ACTH stimulation test results, then continue at current dose. If ACTH stimulation test is abnormal, then study drug should be discontinued. ACTH stimulation test may be waived with sponsor's approval.

Any subject who is withdrawn from the study or has low cortisol levels at the final study visit should be evaluated until full normalization of the hypothalamic-pituitary-adrenal axis occurs. In addition, all subjects should be instructed to carry a card at all times identifying the potential risk for adrenal insufficiency. The card should include the subject's information, the investigator's contact information, and the potential need for glucocorticoids in the settings of shock, surgery, etc.

